subjects received the assigned fixed dose of USVCAP further for 12 weeks (Table 2). Therefore, the overall duration of treatment with USVCAP for subjects in Groups B and C was 13 and 14 weeks, respectively

- End-of-treatment: The end-of-treatment (EOT) for each randomized subject was defined as Day when 12-weeks of twice daily administration of assigned fixed dose of IP was completed by a subject (Table 2 and Table 3)
- Visit 7 was the EOT visit: It was conducted on next day after the subject had completed twice daily administration of assigned fixed dose of IP for 12 weeks (Table 2)
- Post-treatment safety follow-up period: It was of 4-weeks duration after the subject had completed administration of the last dose of assigned fixed dose of IP. Visit 8 was the end-of-study (EOS) Visit in the study.

The Investigator followed the schedule of study assessments and procedures provided in Table 2. A window period of +2 days was allowed at every visit from Visit 3 to Visit 8 and at Visit DE 1 and Visit DE 2.

Pre-study oral anti-diabetic treatment (i.e. monotherapy with metformin hydrochloride) was continued at same dose and regimen from screening up to EOT period. A subject diary was provided to the subjects for recording the IP dosage, capillary glucose measurements, AEs, details on hypoglycaemic episodes, and any change in concomitant medications, as applicable.

The following Standard of Care was provided to each subject throughout the treatment period:

- 1. Step-wise dose escalation in subjects assigned to receive higher doses of USVCAP (i.e. subjects assigned to received fixed dose of 150 IU and 300 IU, BD)
- 2. Pre-study oral anti-diabetic monotherapy (i.e. metformin hydrochloride) continued at same dose and regimen
- 3. Capillary glucose measurements
- 4. Consumption and maintenance of healthy diet and lifestyle regimen
- 5. Treatment for complications related to insulin therapy (e.g. hypoglycaemia, hypokalaemia, etc.) or any other complications as per Investigator's practice and standard treatment guidelines

The Schedule of Study Procedures and Assessments is given in Table 3.

Table 1	Duration	of	Run	in	period(s)	and	treatment	for	doses	of	IP	per	each	Allocated
Treatmo	ent Group													

Treatment Group	Assigned fixed dose of	Treatment duration with assigned fixed	Run-in period/s with lower dose/s of USVCAP	Overall total duration of treatment with			
	USVCAP	dose of USVCAP		USVCAP			
Group A	75 IU BD	12 weeks	Not applicable	12 weeks			

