There was a run-in period/s of 1 week with each lower dose/s prior to initiation of the assigned fixed dose of USVCAP (Table 2). Upon completion of the run-in period/s, the subjects received the assigned fixed dose of USVCAP further for 12 weeks.

The Investigator considered the dose increase for each subject in Group B and Group C only if there was no evidence of lack of tolerability with dose/s of IP prescribed during run-in period/s and that the safety of the subject was unlikely to be compromised after administration of subsequent higher dose/s of the IP.

The dose increase at each DE visit was considered only after laboratory test results for FPG and 2-hour PPG levels were available to the Investigator.

For subjects in Group B (USVCAP 150 IU BD for 12 weeks):

- Run-in period
 - USVCAP 75 IU BD: Day 1 until Day 7
- Treatment period
 - USVCAP 150 IU BD: Day 8 until Day 91

For subjects in Group C (USVCAP 300 IU BD for 12 weeks):

- Run-in periods
 - USVCAP 75 IU BD: Day 1 until Day 7: 75 IU BD
 - USVCAP 150 IU BD: Day 8 until Day 14
- Treatment period
 - USVCAP 300 IU, BD: Day 15 until Day 98

The USVCAP doses were administered as per the trial protocol until the EOT. The subjects were withdrawn from the trial if there was requirement for change in dose during the treatment period (including run-in period and/or assigned fixed dose period), due to any reason(s).

Mode of administration: 1 hour before breakfast and dinner, orally with water

Duration of Treatment:

Treatment period: Each subject was treated with assigned fixed dose of USVCAP (Group A or Group B or Group C) for 12 weeks.

Overall duration of treatment with IP (including run-in period/s):

- Group A=12 weeks
- Group B=13 weeks
- Group C=14 weeks

During the post-treatment follow-up period, subjects were advised treatment for T2DM as per standard treatment guidelines.

Non-investigational Product

It was metformin hydrochloride capsules 250 mg, 500 mg, 850 mg or 1000 mg doses.

Dosage: Subjects continued their pre-study oral anti-diabetic monotherapy (i.e. metformin hydrochloride) as per pre-study dose and regimen from screening until the EOT, the dose adjustment for which, was not allowed during the entire treatment period.

Mode of administration: Orally with water along with meals

Duration of Treatment

• Approximately 17-19 weeks based on the randomized treatment group (i.e. Group A, Group B, or Group C).

Treatment during Post-Treatment Follow-Up Period:

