*NOTE: The term "life-threatening" in the definition of "serious" refers to an event in which the subject was at risk of death at the time of the event; it does not refer to an event, which hypothetically might have caused death if it were more severe.

- Hospitalization is to be considered 'only hospital stay' for ≥ 24 hours. The following hospitalizations should not be reported as SAEs:
- Hospitalization or prolongation of hospitalization needed for procedures required by the clinical trial protocol
- Hospitalization or prolongation of hospitalization as part of a routine procedure followed by the centre
- Hospitalization for a survey visit, annual physicals, or social reasons
- Elective (pre-planned) hospitalizations for a pre-existing condition that had not worsened from baseline (e.g. elective or scheduled surgery arranged prior to start of the study)
- Admissions not associated with an AE (e.g. social hospitalization for purposes of respite care)

Methods and Timing for Assessing, Recording and Analysing Safety Parameters

All AEs and SAEs were collected on eCRFs from the time the subject signs the ICF until the EOS. Any SAE that was ongoing at the time the subject exits the study was followed until the event was resolved or there was a satisfactory explanation, which qualified 1 of the following outcomes:

- Resolved (With residual effects or without residual effects)
- Death
- Unknown (Despite adequate follow-up)

Documentation and Reporting of Immediately Reportable Adverse Events

All SAEs were recorded from the time the subject signed the ICF in the study until the EOS. All SAEs, regardless of causal relationship were reported by the site to sponsor/CRO, the Licensing Authority i.e. the Drugs Controller General of India, and the Chairman of Ethics Committee of the site within 24 hours of occurrence through Appendix XI of Schedule Y.

- Follow-up information on an existing SAE was reported by the Investigator. Appropriate hospitalization or autopsy reports were made available, as applicable. All SAEs were followed-up until resolution (i.e., asymptomatic, stabilization of the event or death)
- The Investigator and sponsor/CRO prepared and submitted a detailed analysed report of all the SAEs to the Head of the Institution where the trial was being conducted, to the Chairman of the Ethics Committee that accorded approval for conduct of the trial and the Licensing Authority within 14 days of occurrence of SAE (as per the Appendix

XI of Schedule Y).

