In this trial, safety analysis was used to perform the safety population (defined above). All safety endpoints were analysed based on descriptive statistics as described above for continuous and categorical variables and presented visit wise. The analysis of safety assessments in this study included summaries of the following categories of safety data collected for each subject.

- Adverse events (AEs)
- Physical examination
- Vital signs
- 12-lead ECG
- Laboratory investigations

Adverse Events

AEs and SAEs were coded by 20.1 version of MedDRA body system and preferred term and tabulated by indicating number and percentage of subjects and number of events. All the AEs were listed and categorized as TEAE and SAE before dosing and after dosing. All AEs, which occur after the first dose of the IP, were categorized as TEAEs i.e. AEs with onset date on or after the first dose of the IP. The TEAEs were tabulated and summarized for each treatment group as; overall TEAEs experienced by subjects during the study, TEAEs experienced by subjects during treatment with actual assigned dose of IP. All AEs were collected, evaluated and tabulated by system organ class (SOC), preferred term (PT), date of onset, relationship to the test drug, seriousness, severity, frequency, action taken, and outcome for each treatment group. Narratives of all SAEs

were presented. AE were compared between treatment groups by using Chi square/Fisher's exact test.

Vital Signs

Descriptive statistics were provided by treatment group for PR, RR, systolic and diastolic BP, and body temperature, etc. The vital signs were generated by visit as absolute values and the change from baseline were recorded. In addition, individual results were reviewed for any treatment-emergent changes of possible clinical significance.

Physical Examination

Descriptive statistics were provided by treatment group for each body system and the change from baseline were also recorded.

12-Lead Electrocardiogram

Descriptive statistics were provided. In addition, individual results were reviewed for any treatment-emergent changes of possible clinical significance.

Laboratory Assessments

Descriptive statistics were provided by treatment group for each clinical laboratory parameter and the change from baseline were also recorded. In addition, individual results were reviewed for any treatment-emergent changes of possible clinical significance.

Concomitant Medications

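### Adverse events are tested across doses on crude percentages, although time on drug is 12, 13 and 14 weeks and the equal-length assigned-dose window starts at different times since first dose

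*Combined protocol and SAP*

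**What the plan says.** The Adverse Events text counts as treatment-emergent all "AEs with onset date on or after the first dose of the IP", so events at run-in doses are included. Events are "tabulated by indicating number and percentage of subjects and number of events". Two summaries by treatment group are planned: "overall TEAEs experienced by subjects during the study, TEAEs experienced by subjects during treatment with actual assigned dose of IP". The section then states that "AE were compared between treatment groups by using Chi square" or Fisher's exact test. The supplied text gives no rate per unit of time, offset or time-to-event method. It does not say which summary the test uses.

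The Overview of Study Design says that "the overall duration of treatment with USVCAP for subjects in Groups B and C was 13 and 14 weeks", and the Duration of Treatment list gives "Group A=12 weeks" for the lowest dose. On collection, the plan states: "All AEs and SAEs were collected on eCRFs from the time the subject signs the ICF until the EOS" (section on methods and timing of the safety assessments). Overall events therefore run on through the post-treatment follow-up to Visit 8.

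Under Investigational Product, the assigned dose is taken on Days 1 to 84 in A, 8 to 91 in B and 15 to 98 in C. In B and C the step up required that the run-in dose had been tolerated, and a subject who needed a dose change, including in run-in, was withdrawn.

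**The concern.** Finding a safe dose is part of the primary objective, and the incidence of treatment-emergent events by group is a stated safety measure. A crude percentage depends on how long, and in which part of treatment, each subject is observed. The two summaries differ from a like-for-like comparison in different ways.

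- **Overall summary.** B and C have one and two more planned weeks on drug than A. Events that occur at 75 or 150 IU during run-in are counted under the higher assigned dose.
- **Assigned-dose summary.** The window is equally long in all groups but opens at first exposure in A, 7 days later in B and 14 days later in C. Only subjects who tolerated the run-in enter it in B and C. A has no such filter.

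A difference between doses could therefore come partly from the design of the window. The choice between the two summaries is open, so it could be made after both are seen.

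**Working it through.** **Inputs from the documents.** Dosing days are as above. Visit 8 is on Day 114, 121 or 128 (Table 2, schedule of assessments). There are 153 subjects randomized 1:1:1, or 51 per group if balanced. The test level is 5% (Statistical Significance). No adverse event rate is given, so every incidence below is an assumption, shown over a range.

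**Step 1: reproduce the exposure.** Days on drug are 84, 91 and 98, which is 12, 13 and 14 weeks as stated. C has 98/84 = 1.167 times A's exposure. The assigned-dose windows are 84 − 1 + 1, 91 − 8 + 1 and 98 − 15 + 1, each 84 days. To Visit 8 the periods are about 114, 121 and 128 days, and 128/114 = 1.123.

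**Step 2: overall summary, identical constant risk.** If A shows incidence p, a group with r times A's time at risk shows 1 − (1 − p)^r.

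| A | Risk only on drug (r = 13/12, 14/12): B, C | Risk continues to Visit 8 (r = 121/114, 128/114): B, C |
|---|---|---|
| 20% | 21.5%, 22.9% | 21.1%, 22.2% |
| 40% | 42.5%, 44.9% | 41.9%, 43.6% |

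With 51 per group and on-drug risk only, a three-group 5% chi-square test of groups with no true dose effect rejects about 5.3%, 6.0%, 6.5% and 7.1% of the time when A's 84-day incidence is 10%, 20%, 30% and 50% (simulation).

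**Step 3: assigned-dose summary.** With constant risk all three windows are 84 days and the timing bias is zero. Now assume that the weekly hazard is 3h in the first two weeks after first dose and h afterwards, with no dose effect. The cumulative hazards in the assigned-dose windows are:

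- A: 3h × 2 + h × 10 = 16h
- B: 3h × 1 + h × 11 = 14h
- C: h × 12 = 12h

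B shows 1 − (1 − p)^(14/16) and C shows 1 − (1 − p)^(12/16). With 20% in A, these are 17.7% and 15.4%. With 40% in A, they are 36.0% and 31.8%. At 30% in A, an early-risk multiple of 2 to 3 gives C minus A of −3.7 to −6.5 points, and the three-group test rejects 6.2% to 9.5% of the time. At 50% in A with a multiple of 3 it rejects about 12%.

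**Step 4: does an exposure-adjusted rate help?** In the same front-loaded case the on-drug hazards from first dose are 16h over 12 weeks in A and 18h over 14 weeks in C. The rate ratio C/A is (18/14)/(16/12) = 0.96. The cumulative-hazard ratios behind the crude tables are 18/16 = 1.13 (overall, on drug) and 12/16 = 0.75 (assigned dose). The rate is much closer to 1 but not exact, because early risk breaks its constant-rate assumption. The first 84 days from first dose give 16h in every group, a ratio of 1.00.

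**The case against.** - **Equal length.** The assigned-dose summary already compares 84 days with 84 days. A reader might infer that neither table covers equal periods. The dosing days contradict that. What stands is the mismatch in time since first dose and in population.
- **Opposite biases.** A reader might also infer that the two tables are necessarily biased in opposite directions. That needs a risk peak after the first dose, which no passage supports. If early risk restarts at each dose step, all three assigned-dose windows carry 16h and the bias disappears.
- **Off-drug follow-up.** The overall table runs to Visit 8, which narrows the gap, as step 2 shows. The larger figures there hold only if there is no risk off drug.
- **Attribution.** Counting run-in events under the randomized group is ordinary analysis by assigned regimen. It becomes a problem only when the result is read as the tolerability of the assigned dose itself.
- **Denominator.** Subjects who leave in run-in may still be in the assigned-dose denominator, since the safety population is everyone randomized and dosed. The text does not settle this. If kept in, they can contribute no event in that window. If dropped, the group is selected for tolerance.
- **Existing safeguards.** Event counts and onset dates are tabulated, safety data are presented by visit, and no stated dose-selection rule depends on the adverse event test. The text also refers to a separate, more detailed SAP, so the tested table may be named there. These points limit the consequence but do not supply a time-at-risk denominator in the supplied text.

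**Conclusion.** The point holds as a modest improvement. The documents confirm unequal time on drug, a test on crude percentages without time at risk, an unspecified choice between two tables, and an assigned-dose window that skips the first one or two weeks on drug in B and C only.

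Under identical constant risk the overall table inflates C over A by about 2 to 3 points at 20% incidence, and the assigned-dose table has no timing bias. Under an assumed threefold early risk the assigned-dose table lowers C by about 4.6 points (20% against 15.4%). Type I error is about 5% to 7% from length alone over 10% to 50% incidence. It is up to about 9.5% with early risk two to three times higher at 30% incidence, and somewhat more at higher incidence. All of this rests on assumed event rates, balanced groups of 51 and full planned exposure. It does not show that the planned comparison would pick the wrong dose.

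**What to change.** 1. Base the between-group comparison of treatment-emergent events and hypoglycaemic episodes on exposure-adjusted rates from first dose in the safety population. Use events per subject-week on drug, and first events per subject-week at risk, in Poisson or negative-binomial models with log time at risk as offset. This also accounts for early withdrawal.
2. Beside it, compare incidence over the first 84 days from first dose in all dosed subjects.
3. Tabulate events by the dose being taken at onset (75, 150 or 300 IU), and report run-in events and withdrawals separately.
4. Keep the crude tables as description. State their denominators, whether follow-up events belong in the assigned-dose table, and which table any chi-square or Fisher's exact test uses.

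The cost is a few more tables and some programming, since onset dates and dosing are already recorded. The model assumes a constant rate. The common window holds less time at the assigned dose in B (84 − 7 = 77 days) and C (84 − 14 = 70 days), so it should sit beside the rate analysis and not replace it. If the analysis is already complete, these should be labelled as unplanned in the clinical study report.

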Study to Evaluate the Safety and Efficacy of Oral Insulin Formulation in Type 2 Diabetes Mellitus Subjects

NCT06473662

06/19/2024

STUDY OBJECTIVES

Primary Objective

To evaluate the safe and effective dose of USVCAP (75 IU, or 150 IU, or 300 IU) after twice daily treatment with selected fixed dose (75 IU, or 150 IU, or 300 IU) of USVCAP for 12 weeks

Secondary Objective

To assess the immunogenicity of the investigational product

INVESTIGATIONAL PLAN

Overall Study Design and Plan-Description

Overview of Study Design

This was a phase IIb, open-label, randomized, comparative study to evaluate the safety and efficacy of USVCAP formulation in T2DM subjects uncontrolled with metformin hydrochloride treatment.

Total of 153 subjects who met the eligibility criteria were randomized in a ratio of 1:1:1 to any one of the following 3 treatment groups:

- Group A: USVCAP 75 IU, BD for 12 weeks
- Group B: USVCAP 150 IU, BD for 12 weeks
- Group C: USVCAP 300 IU, BD for 12 weeks

Each subject had following study periods and visits:

- Screening period (Visit 1): It lasted for up to 21 days after signing the informed consent form (ICF)
- Treatment period (Visit 2 to Visit 7): Eligible subjects were randomly assigned to any one of the above treatment groups at Visit 2 by randomization process through an interactive web response system (IWRS). Each subject from all 3 treatment groups received *assigned fixed dose of USVCAP (i.e. IP) as per allocated treatment groups for 12 weeks.

*Assigned fixed dose in the study is defined as: Fixed dose of USVCAP (i.e. IP) administered to subject twice daily for 12 weeks based on the treatment group (Group A, Group B, or Group C) allocated at randomization visit.

- Upon randomization:
 - Subjects allocated to Group A were prescribed with the assigned fixed dose of USVCAP (75 IU BD) from next day of randomization (Day 1) for 12 weeks
 - Subjects allocated to Group B and Group C, underwent a run-in period of 1 week with each previous lower dose/s, prior to initiation of assigned fixed dose of USVCAP. They additionally visited the study site for a step-wise increase of dose/s at each run-in period/s. These visits were called dose escalation (DE) visits (Visit DE 1 and Visit DE 2) in the trial. The dose increase were done once for Group B and twice for Group C subjects as depicted in Table 2 and Table 3. Upon completion of the run-in period/s, the

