In any case, all study records are for at least 5 years after the completion or discontinuation of the study. The Investigator notified sponsor or its designee of any changes in the archival arrangements, including but not limited to archival at an off-site facility, transfer of ownership of the records in the event the Investigator left the site. Sponsor notified the Investigator in writing when the study-related records were no longer needed.

Statistical Methods Planned in the Protocol and Determination of Sample Size

The following is an outline of the statistical methodology that was used to report and analyse this study. A more detailed description is provided in a separate statistical analysis plan (SAP) that includes additional exploratory analysis not explicitly mentioned in the following sections.

Study Analyses Sets

The analyses was performed on the following trial populations.

- Randomized population: The randomized population consisted of all subjects who were randomized in the study
- Safety population: The safety population consisted of all subjects who were randomized and had received at least one dose of the IP.
- Full Analysis Population: The full analysis set population consists of all the subjects who are randomized into the study, received at least one dose of the IP from the assigned dose by randomization, and had at least one post baseline assessment.
- Per Protocol (PP) population: The per-protocol (PP) population was all the subjects in the FAS population who had completed the study and did not had any major protocol deviation.

Demographic and Other Baseline Characteristics

The demographic variables such as age, gender, ethnicity, body weight and height etc. and baseline status (medical history, physical exam, etc.) was summarized for both PP and full analysis populations.

The descriptive statistics for continuous variables were presented with number (n) of nonmissing observations, missing observations, Mean, Standard Deviation (SD), Median, Minimum and Maximum. For categorical data, descriptive statistics were presented with number of exposed subjects, and number (N) with percentage of observations in the various categories of the endpoint, where percentage were based on the exposed subjects.

Descriptive statistics were provided for body weight, waist circumference and BMI parameters. In addition, individual results were reviewed for any treatment-emergent changes of possible clinical significance.

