Prior and concomitant medications were coded using the standard WHODD dictionary prior to analysis. Counts and percentages were presented by drug class and generic term for descriptive summarization.

Efficacy Analyses

Primary Analysis

The primary endpoint was change in HbA1c level post 12-week administration of selected fixed dose of USVCAP (75 IU, or 150 IU or 300 IU) from baseline visit within each treatment group. The actual measurement of efficacy endpoint was summarized using number of subjects (n), mean, SD, median, and minimum and maximum (range) and 95% confidence interval (95% CI) for each treatment group at both baseline and EOT (End of treatment) visits along with change from baseline to EOT for each treatment group.

The statistical analysis for the primary endpoint were carried out to compare the change in HbA1c post 12-week administration of selected dose of USVCAP from baseline visit within each of the 3 dosing groups by using paired t-test.

In addition to evaluate primary efficacy within each randomly assigned groups as planned, we also evaluated a subgroup analysis on those patients who had uncontrolled hyperglycaemia and those who had not to see the robustness of the data on primary efficacy parameter.

Secondary Analysis

The secondary endpoint of comparing the change in HbA1c post 12-week administration of USVCAP from baseline between the 3-fixed dose groups to examine the dose response relationship between them; analysis of covariance (ANCOVA) with dose groups (treatment groups), visit and interaction between visit and treatment as factors and baseline HbA1c value as covariates using Proc mixed was used. ANCOVA model determined the statistically significant difference between different dose groups on change in HbA1c from baseline to 12-week treatment with USVCAP, controlling for the effect of the baseline HbA1c value as covariate. Also, applying same ANCOVA model and coefficient estimate for dose factor, further pairwise comparisons of the three experimental dose levels for change in HbA1c post 12-week treatment with USVCAP examined the dose response relationship.

Similarly, ANCOVA model were also applied to analyze the change in fasting and postprandial plasma glucose in each treatment group.

Details of the analysis were provided in statistical analysis plan.

Safety Analysis

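### Adverse events get counts, percentages and one between-dose test, but no confidence interval; at about 51 per dose that test misses most doublings from backgrounds up to about 15% and most triplings from up to about 6%

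*Combined protocol and SAP*

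**What the plan says.** The Primary Objective is "To evaluate the safe and effective dose of USVCAP", at 75, 150 or 300 IU, so safety shares the primary question with efficacy.

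Under Safety Analysis, the general rule is descriptive: "All safety endpoints were analysed based on descriptive statistics as described above for continuous and categorical variables and presented visit wise". For categorical data, the section on Demographic and Other Baseline Characteristics defines what that means: "number (N) with percentage of observations in the various categories of the endpoint". It mentions no interval. The Adverse Events subsection adds tabulations by organ class, preferred term, severity, relationship and outcome, narratives for serious events, and one comparison: "AE were compared between treatment groups by using Chi square/Fisher's exact test". It does not say whether the test is pairwise or across all three groups, and it attaches no estimate of the difference.

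HbA1c is treated differently. The Primary Analysis section plans a "95% confidence interval (95% CI) for each treatment group at both baseline and EOT".

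On numbers: "Total of 153 subjects who met the eligibility criteria were randomized in a ratio of 1:1:1". The analysis set for safety is defined as follows: "The safety population consisted of all subjects who were randomized and had received at least one dose of the IP".

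**The concern.** A p-value without an estimate says little about how large a difference between doses could be. Here it is the only inferential statement planned for AEs, in a trial whose sample size was set for the within-dose HbA1c change and not for safety. Two consequences follow.

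- **Low power for uncommon events.** A non-significant comparison of 75, 150 and 300 IU can easily coexist with a real doubling of a modest AE rate.
- **No untreated comparator.** All arms receive the product, so the test's null hypothesis is equal risk across doses. A risk that every dose carries equally satisfies that null whatever its size. Each dose's own incidence is then the relevant evidence, and the plan gives no measure of its precision.

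At stake is how firmly the report can speak about the safety of a dose.

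**Working it through.** **1. The plan's own sizing, for context.** Determination of Sample Size uses a paired t-test with a mean change of 0.5, SD 1.0 at each time, tabled effect size 0.5, two-sided alpha 2.5% and 90% power. An effect size of 0.5 implies an SD of change of 1.0, hence a correlation of 0.5: √(1 + 1 − 2 × 0.5) = 1. The noncentral t distribution gives 89.9% power at n = 52, matching the stated 52. Then 52/0.8 = 65 per group, and 3 × 65 = 195. No safety quantity enters this calculation.

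**2. Inputs for the AE test.**
- Group size: 153/3 = 51. Exact group counts are not given; the planned 65 is shown as a check.
- Alpha: 5%, from Statistical Significance. Two-sided is an assumption.
- Structure: pairwise is an assumption; a three-group version follows.
- AE rates: not in the documents. All rates below are assumptions, shown over a range.

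**3. Power, by exact enumeration.** For risks p1 and p2, power = Σ Bin(a; n, p1) × Bin(b; n, p2) over all tables (a, b) with p ≤ 0.05.

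| Assumed risks | Fisher, n=51 | Chi-square (uncorrected), n=51 | Fisher, n=65 |
|---|---|---|---|
| 5% vs 10% | 7% | 15% | 10% |
| 10% vs 20% | 20% | 29% | 28% |
| 15% vs 30% | 36% | 45% | 46% |
| 20% vs 40% | 53% | 61% | 64% |
| 5% vs 15% | 25% | 39% | 37% |
| 6% vs 18% | 34% | 47% | 47% |
| 8% vs 24% | 50% | 61% | 64% |
| 10% vs 30% | 65% | 73% | 78% |
| 15% vs 45% | 90% | 93% | 96% |

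At 51 per dose, power is below 50% with either test for doublings from up to about 15% and triplings from up to about 6%. Above those backgrounds it is not. At 65 per dose Fisher's test still misses the same cases more often than not, so enrolling 153 instead of 195 is not the main cause.

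**4. Three-group chi-square at 51 per dose (40,000 simulations).** Power is 44% for 5/5/15%, 29% for 5/10/15%, 30% for 10/10/20% and 79% for 10/10/30%. The pattern is the same.

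**5. Shared harm.** If every dose has a 20% risk, the pairwise test is significant in 3% (Fisher) to 5% (chi-square) of trials. That is its false-positive rate, as it should be under a true null, and it is not a signal of the 20% risk.

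**6. What intervals would add.**
- One dose, no events: the exact two-sided upper 95% limit is 1 − 0.025^(1/51) = 7.0%. For 5/51 it is 21.4%.
- Two doses, 5/51 (9.8%, Wilson limits 4.3 to 21.0%) against 10/51 (19.6%, Wilson limits 11.0 to 32.5%): the difference is 9.8 points and Fisher p = 0.26. The Newcombe lower limit is 9.8 − √[(19.6 − 11.0)² + (21.0 − 9.8)²] = −4.3. The upper limit is 9.8 + √[(32.5 − 19.6)² + (9.8 − 4.3)²] = +23.8. So a clearly non-significant p-value is compatible with an excess of more than 20 points.

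**The case against.** The sponsor can fairly say that this criticises an auxiliary line. Discussion of Study Design says that safety is determined by the incidence and severity of treatment-emergent events, including hypoglycaemia, and by laboratory change. The safety tables are per dose, and a 20% risk in every arm would be visible in them. Anyone can compute an interval from the tabulated counts. Descriptive AE tables with a supplementary Fisher test are ordinary in a phase IIb trial. The statistical section also calls itself an outline and refers to a separate, fuller SAP.

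Much of this stands, and it rules out three stronger readings that a reader might infer.

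- *That dose safety rests on p-values.* It does not; the safety analysis is mainly descriptive and the test is an addition.
- *That the plan treats a non-significant test as proof of safety.* No passage says so. What is missing is an interval, or any statement on interpretation, that would guard against that reading.
- *That the test misses doublings and triplings in general.* It does not. A tripling from 10% is detected 65–73% of the time, a tripling from 15% about 90%, and a doubling from 20% 53–61%.

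The absence of intervals can be asserted only for the text available. The objection does not explain why HbA1c gets a 95% interval while the safety half of the same objective gets none.

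**Conclusion.** The point holds as an improvement worth making, not as an error that invalidates an analysis. In the available text, no AE has a planned interval, upper limit or risk difference, and the one between-dose test is weak where AEs are uncommon: Fisher power is 7–36% for doublings from 5–15% and 25–34% for triplings from 5–6%. It is adequate or good for large relative increases from common backgrounds. Being a comparison among active doses, it carries no information on a harm they share. Per-dose incidence does carry it, but with about 51 patients that incidence is imprecise, and the plan does not show how imprecise.

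The size rests on 51 per dose, two-sided 5%, pairwise testing and assumed background rates. The argument about shared harm needs none of these except that all arms are active.

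**What to change.** In Safety Analysis – Adverse Events, for any treatment-emergent AE, related treatment-emergent AEs, serious AEs, treatment-emergent AEs leading to withdrawal, and hypoglycaemia, report:

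- each dose's incidence with an exact (Clopper–Pearson) 95% confidence interval;
- pairwise risk differences (150 − 75, 300 − 75 and 300 − 150 IU) with Newcombe 95% confidence intervals.

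Keep the chi-square/Fisher p-values as descriptive, and add a sentence that a non-significant result is not evidence that the doses are equally safe. If these analyses are added after the SAP, label them post hoc in the clinical study report, as Procedures for Reporting Deviations from Original Statistical Plan requires.

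The cost is a sentence or two of wording and a few extra table columns. No new data or patients are needed. The downside is presentational: the intervals will be wide (an upper limit of at least 7.0% per dose at 51 patients) and will look less reassuring than bare percentages.
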